### **9.1.13 Patient Diary**

Seizure information will be collected through an IVRS telephone diary completed daily throughout the study. The patient or their caregiver will also complete a paper diary daily to record daily IMP dosing volumes, usage of rescue medication, concomitant AEDs and AEs throughout the study. Patients' meal times the day before and the day of Visit 2 and Visit 8 will also be recorded in the paper diary. Seizure counts over 99 for any specific seizure type may also be collected in a paper diary.

The number and type of convulsive and non-convulsive seizures as well as information on usage of rescue medication, concomitant AEDs and AEs will be collected each day from screening (Visit 1) until completion of dosing or withdrawal (Visit 8/Withdrawal visit or Visit 9, as applicable). Information on IMP intake will also be recorded each day from randomization (Visit 2) until completion of dosing or withdrawal (Visit 8/Withdrawal visit or Visit 9, as applicable).

### **9.1.14 Investigational Medicinal Product Accountability**

IMP will be dispensed at each of the following visits:

- Visit 2 (Day 1).
- Visit 4 (Day 29).
- Visit 6 (Day 57).
- Visit 8 (Day 99) (for patients not entering the OLE study on Day 99; if required).

Patients will be asked to return all IMP (used and unused) to each relevant visit (Visits 4, 6, 8 and 9). The site will check the returned IMP against the usage recorded using the IVRS report and diary. Any discrepancies will be discussed with the patient/caregiver and documented accordingly within the patient's source documents.

Refer to [Section 9.1.16.2.1](#) for the list of 'Triggering Drug Accountability Discrepancies' associated with monitoring of drug abuse liability.

### **9.1.15 Adverse Events**

Any adverse changes in the patient's medical condition, following completion of the consent/assent form by the patient, will be recorded on the CRF as AEs, questioning the patient further if necessary. All AEs occurring during the study, whether or not attributed to the IMP, observed by the investigator or reported by the patient will be recorded in the CRF.

SAEs must be reported to GW Pharmacovigilance Department (PVD) within 24 hours of discovery or notification of the event, and recorded in the CRF.

Refer to [Section 12](#) for definitions, procedures and further information.

The number of inpatient hospitalizations that are, in the investigator's opinion, due to epilepsy will be recorded in the patient's CRF and through the SAE reporting process.

Refer to [Section 9.1.16.1.1](#) for the list of 'Triggering AEs of Interest' associated with monitoring of drug abuse liability.

### **9.1.16 Monitoring of Drug Abuse Liability (for Patients 12 Years of Age and Older)**

There are two triggers that will require the investigator or study coordinator to discuss abuse potential signals with the patient or their caregiver. These are either AEs of interest that may be reported by the patient/caregiver, or drug accountability issues regarding overuse of the IMP or missing bottles. Different questionnaires will be completed by the site depending upon which trigger occurs (see [Figure 9-1](#)). Irrespective of the above, all patients/caregivers will be interviewed at their final dosing visit (Visit 8/Withdrawal visit or Visit 9, as applicable) and a Study Medication Use and Behavior Survey will be completed by the investigator or study coordinator. Investigators and study coordinators will be provided with training on how to complete and perform the processes outlined in this section. This training must be completed and documented by the relevant site staff prior to implementation at site.

#### **9.1.16.1 Monitoring of Adverse Events**

AE information will be collected according to [Section 9.1.15](#).

##### **9.1.16.1.1 List of 'Triggering Adverse Events of Interest'**

During the collection of AEs, if the patient reports an AE consistent with any of the following categories, then the investigator or study coordinator is required to complete an

additional Supplemental Adverse Event Form and a Site Classification Form (investigator only) following further discussion of the event(s) with the patient or their caregiver. The categories are:

- Euphoria or inappropriate elation.
- Inappropriate laughter or exhilaration.
- Mood changes.
- Drunk, high or intoxicated.
- Hallucinations (visual or auditory), dissociations, disorientation, agitation.
- Disturbance in cognition, memory, or attention.
- Drug abuse.
- Drug withdrawal or drug withdrawal syndrome.
- Addiction.
- Overdose.
- Misuse of IMP.
- Thoughts of suicide, attempted suicide or suicide.

An AE that is consistent with the above categories will be known as a ‘triggering AE of interest’ for the purposes of this study.

#### **9.1.16.1.2 Supplemental Adverse Event Form**

This form consists of 15 questions regarding the AE and use of IMP. It is completed as part of an interview with the patient/caregiver when a triggering AE of interest is reported. It is important that this is completed by a trained investigator or study coordinator with the patient/caregiver present. The answers on the Supplemental Adverse Event Form will then be transcribed into the patient’s CRF for the study. If the Supplemental Adverse Event Form cannot be completed at the time the triggering AE of interest is reported, then the site should contact the patient/caregiver to obtain the required answers as soon as possible.

### **9.1.16.2 Monitoring Drug Accountability Discrepancies**

Any time after enrollment until final collection of study data, drug accountability discrepancies are monitored as follows:

- At routine Drug Accountability collection times (i.e., Visits 2, 4, 6 and 8): the site personnel will collect the IMP clinical supplies and make sure the usage is in line with the expectations reported within the IVRS report and paper diary.
- At any time that the site is informed by either the IVRS or by the patient/caregiver about any overuse of IMP, suspected misuse, abuse, or diversion.

#### **9.1.16.2.1 List of ‘Triggering Drug Accountability Discrepancies’**

If there are any discrepancies in drug accountability as outlined by the criteria below, known as ‘triggering drug accountability discrepancies’, then the trained investigator or study coordinator will complete a Supplemental Drug Accountability Form and Site Classification Form (investigator only) following further discussion of the event(s) with the patient/caregiver. The triggering drug accountability discrepancies are as follows:

- Missing bottle(s).
- Compliance issues where one or more bottles are used compared to what was the expected use, according to the IVRS report and paper diary.
- Returned IMP supply with evidence of tampering.
- Greater than the target daily dose as recorded in the IVRS report and paper diary.

#### **9.1.16.2.2 Supplemental Drug Accountability Form**

This form consists of eight questions regarding various aspects of drug accountability and patient usage. It is completed as part of an interview with the patient/caregiver when a triggering drug accountability discrepancy is identified. It is important that this is completed by a trained investigator or study coordinator with the patient/caregiver present. The answers on the Supplemental Drug Accountability Form will then be transcribed into the patient’s CRF for the study. The accountability reporting procedures will still occur. If the Supplemental Drug Accountability Form cannot be completed at the time the triggering drug accountability discrepancy is identified, then the site should contact the patient/caregiver by telephone to obtain the required answers as soon as possible. (Note: IMP refers to GWP42003-P or placebo, not other concomitant medications).

### **9.1.16.3 Site Classification Form**

The investigator should review the applicable Supplemental Adverse Event Form or Supplemental Drug Accountability Form, and then complete the Site Classification Form. For each Supplemental Adverse Event Form or Supplemental Drug Accountability Form completed, there should be an associated Site Classification Form.

The Site Classification Form requires the investigator to assign the finding to an appropriate classification and then to also assign the possible relationship to the IMP. The investigator is also required to indicate the level of the certainty of the classification. The answers from the Site Classification Form will then be transcribed into the patient's CRF for the study.

### **9.1.16.4 Study Medication Use and Behavior Survey**

This form consists of 18 questions regarding the use of the IMP. The trained investigator or study coordinator will complete this survey as an interview with the patient/caregiver at the final dosing visit (Visit 8/Withdrawal visit or Visit 9, as applicable). The answers on the Study Medication Use and Behavior Survey will then be transcribed into the patient's CRF for the study.

The Study Medication Use and Behavior Survey will be completed for all patients 12 years of age and older in the study and not only those that have reported a triggering AE or drug accountability discrepancy.

### **9.1.16.5 Adjudication Committee: Assessment of Abuse Potential of GWP42003-P**

Any triggering AE or triggering drug accountability must be notified to the GW PVD using the same fax number for SAE reporting within 24 hours of becoming aware of the event.

A formal Adjudication Committee will be appointed and assigned to this initiative to classify triggered cases. The Adjudication Committee will meet on a periodic basis to review and assess all of the information collected on triggered cases. Only data from patients who have completed the study will be assessed.

[figure not shown]
A detailed charter will be agreed, which will describe the roles, responsibilities and duties of the members of Adjudication Committee. The Committee will review all of the information collected in the process and in the assessment of the abuse potential of GWP42003-P, such as:

- All triggering AE information.
- Supplemental Adverse Event Form (if applicable).
- All triggering drug accountability discrepancies.
- Supplemental Drug Accountability Form (if applicable).
- Site Classification Form.
- Study Medication Use and Behavioral Survey.
- Additional information from site(s) as requested by the Committee.

The Adjudication Committee will assess all of the information. It will form a position on the classification of each event and will write a study-related report, detailing the conclusions and recommendations.

The overall process is summarized in [Figure 9-1](#).

**Figure 9-1 Flow Diagram for Identifying and Evaluating Clinical Trial Adverse Event Data Through Systematic Categorization, Tabulation and Analysis which can Illuminate an Abuse Potential Signal (for Patients 12 Years of Age and Older)**

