**Monitoring of Drug Abuse Liability (for patients 12 years of age and older):**

[figure not shown]
During the routine collection of AEs in this study, if AEs are reported which can illuminate an abuse potential signal (specific AEs

	
detailed in Section 9.1.16.1.1), then the investigator or study coordinator is required to complete an additional Supplemental Adverse Event Form and a Site Classification Form (investigator only) following further discussion of the event(s) with the patient/caregiver.
 
The second trigger that will require the investigator or study coordinator to discuss abuse potential signals with the patient/caregiver is drug accountability issues regarding overuse of the IMP or missing bottles.
 
Irrespective of the above, all patients/caregivers will be interviewed at their final dosing visit (Visit 8/Withdrawal visit or Visit 9, as applicable) and a Study Medication Use and Behavior Survey will be completed by the investigator or study coordinator.
 
A formal Adjudication Committee will be appointed and assigned to this initiative to classify triggered cases. The Adjudication Committee will meet on a periodic basis to review and assess all of the information collected on triggered cases.

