#### **9.1.11 Interactive Voice Response System**

The IVRS will be used to collect patient reported diary data (refer to [Section 9.1.13](#)), to assign patients to treatment groups and to provide treatment allocation information in the event of patient unblinding. The IVRS will also be used to manage IMP supply.

A member of the study team must contact the IVRS at each clinic visit in order to:

- Obtain a patient's screening number (Visit 1).
- Randomize a patient and obtain their patient number (Visit 2).
- Obtain dispensing information (Visits 2, 4, 6 and 8).
- Provide completion/taper/premature termination information (Visit 8/Withdrawal visit or Visit 9, as applicable).

Training will be given to all sites prior to the start of the study.

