The CWS/PCWS will be used at Visit 2, to establish a baseline score, and then again at Visit 9, the safety follow-up telephone call on day 123 ( $\pm 3$ ) and Visit 10 for any patient completing the study or withdrawing early (see [APPENDIX 1](#)). Patients entering the OLE on the day of Visit 8 will continue taking IMP; in this instance withdrawal will be evaluated at the end of their participation in the OLE. For patients who delay entry into the OLE study, Visit 9 should occur on the day the patient enters the OLE study (and within seven days of Visit 8) and will include CWS/PCWS.

Assessments will be conducted only if patients are of an appropriate age (four years of age and older).

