All IMP (used and unused) will be collected and a check of the returned IMP against usage should be made. For patients who withdraw early, the IVRS will be contacted to confirm withdrawal from the study. Patients who withdraw should have their dose of IMP tapered gradually (10% each day) over a period of 10 days, beginning at the time the decision is made to discontinue. In some cases, tapering the dose of IMP may be inadvisable (e.g., continued dosing is not possible due to an AE). The decision on whether or not to taper IMP will be left to the investigator's clinical judgment. If the tapered dose is administered, the IVRS will be contacted to generate the patient's daily IMP dosing volumes, confirm start of the 10-day taper period and for additional treatment pack assignment. Patients should continue to complete the IVRS and paper diary and should return for the 'End of Taper Period' visit, if possible.

Patients who have completed all of the scheduled study visits will be offered the option of entering an OLE study. Entry is to be on the same day as Visit 8 (Day 99) or within seven days of Visit 8.

For patients who enter the OLE study on Day 99, the IVRS will be contacted to confirm the patient's completion of this study and the paper diaries will be collected. For patients 12 years of age and older, the trained investigator or study coordinator will complete the Study Medication Use and Behavior Survey as an interview with the patient/caregiver.

For patients not entering the OLE study on Day 99, the IVRS will be contacted to confirm start of the 10-day taper period and for additional treatment pack assignment (if required). The IVRS will generate the patient's daily IMP dosing volumes for the 10-day

taper period; patients will then receive sufficient IMP and a dosing regimen as assigned by the IVRS for the taper period. During this time IVRS and diary information will continue to be recorded. The taper period may be interrupted if the patient wishes to enter the OLE study within the seven-day timeframe.

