Study Medication Use and Behavior Survey #									X		

\* To be performed for all patients completing or withdrawing from the study. Patients who complete treatment but do not enter the OLE study on Day 99 will commence a 10-day IMP taper period, which may be interrupted at any time within seven days if the patient subsequently opts to participate in the OLE study. Patients who withdraw early should commence the 10-day IMP taper period, if possible.

\* Only required for those patients who delay entry into or do not participate in the OLE study or for those who withdraw from the study early and taper IMP. Visit 9 should be within seven days of Visit 8 for patients delaying entry to the OLE study. For patients who complete treatment but do not participate in the OLE study, Visit 9 should be 10 (+3) days after Visit 8. For patients who withdraw early and taper IMP, this visit should occur 10 (+3) days after the Withdrawal visit. Patients who opt not to enter the OLE study or who withdraw early must have weekly (±3 days) safety telephone calls until Visit 10.

\*\* For patients who do not enter the OLE study or who withdraw from the study early; can be conducted by telephone.

† Sample can be taken at any clinic visit during the study.

▲ Vital signs and ECG must be re-assessed 2-3 hours post dose.

♥ Only required for patients who opt not to enter the OLE study or who withdraw from the study early (including withdrawal during the taper period).

∞ Urine sample taken if possible.

‡ Urine dipstick pregnancy test at Visit 2; serum sample test at Visits 1, 2 and Visit 8/Withdrawal visit.

[figure not shown]
- ^ For patients  $\geq 20$  kg: blood samples collected pre-dose and at 2–3 hours and 4–6 hours post-dose; there must be a minimum period of at least two hours between each of the three blood sampling time-points.
- ^^ For all patients, provided the risk/benefit outcome is favorable in the investigator's opinion. Blood samples taken prior to administration of IMP. Patients are to record the dosing time of their concomitant AEDs in the diary.
- ◇ Blood samples must be taken at the same time intervals as at Visit 2.
- ¶ Caregivers are to compare to the memory aid from Visit 2.
- ▲ Completion of memory aid; to be referred back to at subsequent assessments.

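### The rule that the abuse-potential Committee assesses only patients who completed the study can be read as excluding withdrawn patients' triggered cases; it should say that it is a timing rule, if that is what is meant

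*Protocol*

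**What the plan says.** Protocol Section 9.1.16 sets up abuse-liability monitoring for patients aged 12 or older. There are two kinds of trigger: adverse events of interest (9.1.16.1.1) and drug accountability discrepancies (9.1.16.2.1). Each leads to a supplemental form and an investigator's Site Classification Form. A Study Medication Use and Behavior Survey is completed for all patients in this age range at the final dosing visit, which may be the Withdrawal visit (9.1.16.4).

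Section 9.1.16.5 gives the triggered cases to an Adjudication Committee that meets periodically. The synopsis describes the same task, to "review and assess all of the information collected on triggered cases", with no limit on whose cases count. Section 9.1.16.5 adds the limit: "Only data from patients who have completed the study will be assessed". Later in the same section the Committee is told to assess all of the information, and: "It will form a position on the classification of each event". It then writes a report with conclusions and recommendations.

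Having completed the study is not a defined term. The Definition of Terms covers end of treatment, which expressly includes withdrawal, and end of study.

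**The concern.** The limiting sentence can mean two things. It may say when a case is ready for review, or it may say whose cases are reviewed. Under the second meaning, a triggered case in a patient who withdrew never reaches the Committee.

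That exclusion would not be neutral. Protocol Section 10 allows a patient to be withdrawn for any evidence of drug abuse or diversion, and for type four or five suicidal ideation or behavior. Drug abuse and suicidal thoughts or acts are on the trigger list in 9.1.16.1.1, and suspected abuse or diversion is monitored under 9.1.16.2. An event that prompts the Committee's interest can therefore also be the reason the patient does not complete. A report limited to completers would be selected on a possible consequence of the signal it is meant to judge, and could under-represent the cases that ended participation.

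**Working it through.** No arithmetic applies. The question is which meaning the text supports, so the relevant places are set side by side.

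**Places that separate completing from withdrawing, and so support a completers-only meaning**

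- Protocol 9.1.11: site staff must "Provide completion/taper/premature termination information", with completion and premature termination as distinct entries.
- Protocol 9.1.12.10: the withdrawal scale is used again at several points up to "Visit 10 for any patient completing the study or withdrawing early".
- Protocol 9.2.8: "For patients who withdraw early, the IVRS will be contacted to confirm withdrawal from the study".
- Protocol Appendix 1, footnote: "To be performed for all patients completing or withdrawing from the study".
- Protocol 13.3: the per-protocol set takes patients who complete the study, and SAP 5.2.3 accordingly leaves out those who withdrew during the treatment phase.

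**Places that support a timing meaning**

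- Protocol 9.1.16.5: the limiting sentence directly follows the statement that the Committee meets periodically, where a rule about when a file is ready would be natural.
- Protocol 9.1.16 and 9.1.16.4: the survey is one of the Committee's inputs, and is collected at the Withdrawal visit as well as at Visit 8 or 9.
- Protocol 9.2.9: at Visit 9 the IVRS is contacted to confirm completion of the study, and that visit is also attended by patients who withdraw early and taper.

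**Fit with the remit.** Under the timing meaning, all information and each event are still assessed, only later, and no case is lost. Under the completers-only meaning, events in withdrawn patients get no Committee position, contrary to the plain sense of the instruction to take one on each event.

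**Does the Visit 9 usage settle it?** Not fully. Among early withdrawals, Visit 9 is required only for those who taper. Section 9.2.8 leaves tapering to the investigator's judgment. A patient who withdraws without tapering is registered only as a withdrawal.

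**What is unaffected under either meaning**

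- Every triggering event is notified to the sponsor's pharmacovigilance department within 24 hours (Protocol 9.1.16.5).
- The investigator still classifies each case (Protocol 9.1.16.3).
- The SAP summaries of the survey, supplemental forms and Site Classification Form (5.7.4 to 5.7.7) and the adverse event listings (5.6.2) have no completer restriction.

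**Size.** The number of unadjudicated cases is zero under the timing meaning. Under the completers-only meaning it is the number of triggered cases in withdrawn patients. The documents give neither an expected number of triggered cases nor a withdrawal rate, so it cannot be computed.

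**The case against.** The strongest reply is that the timing meaning is the intended one. Periodic meetings during a running trial need a rule for when a file is complete. Collecting a Committee input at the Withdrawal visit makes little sense if withdrawn patients are never reviewed. Tapering is the default after withdrawal, so most early withdrawals would be expected at Visit 9, where the protocol itself records completion. A charter is to govern the Committee and Figure 9-1 summarizes the process. Neither is in the text available for review, and either may settle the matter.

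Much of this stands. The timing meaning is plausible and may well be what was intended, and the charter and figure are not counted as missing. But no passage states the rule. The survey is collected from all patients aged 12 or older and summarized under SAP 5.7.4 in any case, so its collection at withdrawal does not show that withdrawn patients are adjudicated. The Visit 9 usage leaves out withdrawals who do not taper.

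It can also be said that the limiting sentence is simply a specific scope clause qualifying the general remit. That is possible too, which is why the text shows an unclear scope and not a proven contradiction.

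**Conclusion.** The wording should be corrected, at low severity. Read literally and with the protocol's usual vocabulary, the sentence keeps withdrawn patients' triggered cases from the Committee, which does not fit its task and would select on a possible consequence of the event. This rests on taking completion in its usual protocol sense. If the sentence is a timing rule, nothing is lost and only the wording is at fault.

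A reader might infer more than the documents support:

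- That the plan definitely excludes withdrawn patients. It does not say so, and the timing meaning remains open.
- That the loss can be gauged by counting how many withdrawal reasons overlap with triggers. That counts items on a list, not patients.
- That the absence of Committee results from the SAP's tables and listings shows withdrawn patients are dropped. The SAP carries no Committee output for completers either; the Committee writes its own report.
- That safety data on withdrawn patients disappear. Notification, site classification and the SAP safety summaries all continue.

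The effect is confined to the Committee's adjudication and report, for patients aged 12 or older. No efficacy analysis is touched.

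**What to change.** Replace the limiting sentence in Protocol 9.1.16.5 with:

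> All triggered cases under Section 9.1.16 will be assessed, including those in patients who withdraw; each case is reviewed once the patient has completed or withdrawn from the study.

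Make sure the Committee's charter says the same. If the sponsor does intend a completers-only limit, the protocol should say so, give the reason, and reconcile it with the instruction to take a position on each event.

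The cost is a small amendment under Protocol 16.1 (investigator agreement, with the ethics committee or review board informed and its approval needed only if the change is substantial) and a few more cases for the Committee to review. No new data are needed, because the supplemental forms are completed when a trigger occurs and the survey at the Withdrawal visit. No withdrawal rule or age limit changes. SAP 5.2.3 shows that the blinded data review has already been held. If an amendment is therefore too late, stating the rule in the charter and in the Committee's report achieves the same.
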